9.2.1.4 Site(s) Performing Correlative Study

All study sites involved in the study will perform PK analysis.

9.2.2 Tissue analysis of HSP90 clients

9.2.2.1 Collection of Specimen(s)

Optional tumor biopsies will be performed pretreatment and one week (+/- 3 days) after commencing therapy with the combination as part of the phase I dose escalation and dose expansion cohorts. Only lesions that are deemed biopsiable through minimal risk procedures will be selected. For each biopsy, if possible, four core biopsy passes will be made. The first and third cores of tissue will be placed in formalin and then fixed in paraffin. The second and fourth cores of tissue will be flash frozen in liquid nitrogen and embedded in OCT. The first core will be used for IHC and primary outcome assessment. The second core will be used for gene and protein expression analysis. The third and fourth cores will be used to augment testing of cores 1 and 2, should the first and/or second cores be exhausted, and will be stored for future

analysis.

9.2.2.2 Handling of Specimens(s)

As described above, four cores will be obtained and fixed. The SOP for collection, handling, and processing is attached (Appendix I). Samples will either be stored at the individual sites and sent in batch at the time of planned correlative study analysis or sent to and stored at the [name] Laboratory at MGH. FFPE samples will be stored at room temperature. Frozen samples will be stored in a -80 degree freezer.

9.2.2.4 Site(s) Performing Correlative Study

All sites are expected to participate in these correlative studies.

9.2.3. Blood-BRAF Assay

9.2.3.1 Collection of Specimen(s)

Samples will be obtained via venipuncture at the time of safety lab collection. One 10 mL green top (heparinized) tube and 1 serum separator will be required to be collected at the following time points:

- Pretreatment
- Following the one week lead-in of AT13387
- Cycle 1, day 15 (in phase I study)
- Day 1 of every cycle of therapy

- At the time of progression

9.2.3.2 Handling of Specimens(s)

Specimens will either be processed on site using the collection and processing SOP (Appendix I) or shipped to the [name] Laboratory overnight for processing and storage. Following processing, samples will be stored in a -80 degree freezer until batch analysis is performed.

9.2.3.4 Site(s) Performing Correlative Study

All study sites are expected to participate in this correlative study.

10. STUDY CALENDAR

Baseline evaluations are to be conducted within 14 days prior to start of protocol therapy. Scans and x-rays must be done \leq 4 weeks (28 days) prior to the start of therapy. Patients who are not being treated with AT13387 do not need to have Day 8 and Day 15 assessments done. In the event that the patient's condition is deteriorating, laboratory evaluations should be repeated within 48 hours prior to initiation of the next cycle of therapy. Participants will be required to maintain a diary (Appendix D) during each cycle and to bring the diary, unused pills, and all medication bottles to the day 1 visit of each cycle.

Procedure	Pre-Study	Cycle 1			Cycles 2+			End of Txt Visit	28 Day F-U Visit ³
	Baseline ¹	Day 1 ^{2,b}	Day 8 ⁴	Day 15 ⁴	Day 1 ²	Day 8	Day 15		
Dabrafenib and Trametinib ^A		DT ----- DT							
AT13387 ^B		X	X	X	X	X	X		
Informed Consent ^a	X								
Demographic	X								
Medical History	X	X	X	X	X				
Concurrent Medication	X	X	X	X	X				
Serum pregnancy test (B-Hcg) ^c	X								
Physical Examination	X	X	X	X	X			X	
Vital Signs (BP, HR, body temperature)	X	X	X	X	X	X	X	X	
ECOG Performance Status	X	X	X	X	X	X	X	X	
Dermatology Examination ^d	X				X				
Height	X								
Weight	X	X			X			X	
Ophthalmology Examination ^e	X				X				
12 Lead EKG ^f	X	X	X	X	X	X	X		
Hematology/Clinical Chemistry ^{g,p}	X	X	X	X	X	X ^p	X ^p	X	
Echo/MUGA ^h	X				X				
Coagulation ⁱ	X								
Tumor Measurements ^j	X								
Radiological Examination ^j	X							X ^j	
PK Analysis ^k		X		X					
Biopsies ^l	X		X					X	
Blood BRAF testing ^m		X		X	X			X	
AE assessment ⁿ	X	X	X	X	X	X	X	X	X
Long term Follow up ^o									

A. Dabrafenib and Tramatinib: doses as assigned; Dabrafenib BID and Trametinib QD.

B. AT13387: dosing as assigned per dose level.

1. All Prestudy assessments must be completed within 14 days prior to first dose, except for Scans and Echo that must be done within 28 days prior to first dose.

2. Assessment throughout the study is calendar based starting from first day of dosing (Day 1) in the first cycle of treatment. Dose interruptions should not alter the assessment schedule for any subsequent treatment cycle. Assessments and administration of study medication for each visit can be done within 3 days of the projected visit date. However, there must always be at least 6 days between AT13387 infusions.
3. Follow up visits should be 28 days from last dose of study drugs (\pm 3 days).
 - a. Informed Consent can be obtained 28 days prior to the first dose
 - b. If within 3 days of screening, this assessment does not need to be repeated on Day 1 of the first dose
 - c. Serum Pregnancy test (Woman of childbearing potential only) done within 72 hours of first dose.
 - d. Dermatological Examination done at screening and then every 8 weeks (2 cycles)
 - e. Ophthalmological examination is done at screening, week 4, and annually; additional ophthalmic exams will be performed only as symptomatically warranted
 - f. Triple EKG will be collected at intervals according to the treating institution's standards prior to each AT13387 infusion
 - g. sodium, potassium, carbon dioxide/bicarbonate, BUN creatinine, glucose, calcium, magnesium, phosphorus, AST, ALT, total Bilirubin, Alkaline phosphatase, total protein and albumin, LDH, hematology includes CBC with differentials and platelets
 - h. Echo/MUGA is done at screening, week 4, week 12, week 24 and every 12 weeks thereafter.
 - i. Includes PT, PT-INR, PTT, repeated as indicated
 - j. Tumor measurements and radiological exam done every other (odd) cycle within 7 days of day 1 treatment. Documentation (radiologic) must be provided for patients removed from the study for progressive disease. Brain CT/MRI is required at baseline for patients with melanoma.
 - k. PK for phase 1: Cycle 1 Days 1 and 15; pre, 1, 2, 4, 6, 8, 24 hour post dose, Day 1 in Cycles 2, 4, 8, and 12.
 - l. In patients with biopsiable disease; pre treatment, Cycle 1 Day 8 (+/- 3 days), at disease progression (if possible)
 - m. Blood BRAF analysis performed C1 D1, C1 D15, at the beginning of each subsequent cycle and at disease progression.
 - n. AE assessment starting from the day 1 of dosing throughout the study
 - o. After 28 day follow up visit, patient is followed for survival only. Survival status is to be collected every 6 months (+/- 2 weeks) for up to 2 years and can be completed by phone. Patients removed from study treatment for any reason other than progressive disease will be followed until disease progression or death, whichever occurs first.
 - p. After cycle 6, hematology/clinical chemistry are collected on Day 8 and Day 15 at the investigator's discretion.
4. Physical Exam, Medical History, Concurrent Medications, Vital Signs, ECOG Status, Hematology and Blood Chemistry panels will be completed prior to Day 8 and Day 15 treatment. Day 8 and Day 15 assessments are not required for patients who are not receiving AT13387 infusions.

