5.2 Definition of Dose Limiting Toxicity

Dose-limiting toxicity (DLT) is based on the CTEP Active Version 5 of the NCI Common Terminology Criteria for Adverse Events (CTCAE). DLT refers to toxicities experienced during the first cycle of treatment between days 1-28. A DLT must be considered to be at least possibly related to study drug(s) will be defined as follows:

- Any grade 4 toxicity
- Grade 3 (or grade 2 intolerable) non-hematologic toxicity
- Grade ≥ 3 neutropenia with fever $> 38.5^{\circ}\text{C}$
- Grade 3 thrombocytopenia with clinically significant bleeding
- Furthermore, grade 2 intolerable/grade 3 fatigue that results in hospitalization should be considered a DLT.
- Intolerable AEs are toxicities deemed to lead to a missing dose of AT13387 or more than 25% of dabrafenib/trametinib in the first cycle.

In general, all Grade 3 or intolerable grade 2, non-hematological toxicities regardless of duration are considered DLT. However, the following Grade 3 toxicities will not be considered a DLT.

- The appearance of cutaneous squamous cell carcinoma or keratoacanthoma will not be considered a dose limiting toxicity as these are commonly observed with dabrafenib.
- Grade 3 fatigue persistent for ≤ 7 days
- Grade 3 nausea, vomiting, or diarrhea persisting ≤ 72 hours with maximum supportive care
- Grade 3 electrolyte events if they are resolved with replacement within 24 hours
- Lymphopenia regardless of grade
- The following grade 3 laboratory abnormalities will not be considered dose limiting if they return to baseline within 7 days: elevated bilirubin, AST, ALT, cholesterol, amylase, lipase, creatinine and hypertriglyceridemia

Management and dose modifications associated with the above adverse events are outlined in Section 6.

Dose escalation will proceed within each cohort according to the following scheme. Dose-limiting toxicity (DLT) is defined above.

Table 5.2. Dose escalation table

Number of Patients with DLT at a Given Dose Level	Dose Escalation Rule
0 out of 3	Proceed to the next dose level and enroll 3 patients
1 out of 3	Enroll and treat 3 additional patients at this dose level.
≥ 2 out of 3	Dose escalation will be stopped. The MTD will be one dose below this dose level. Three (3) additional patients will be entered at the next lower dose level if only 3 patients were treated previously at that dose.
1 out of 6	Proceed to the next dose level.

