9.2.1.2 Handling of Specimens(s)

For each sample, the date and time of the dose and the date and time of the PK sample draw will be recorded and keep as Source Documentation in each individual patients chart.

Details for AT13387 PK collection and process are provided in the “AT13387 Pharmacokinetic Laboratory Manual.”. Note: This manual will be disseminated with the clinical protocol and is also available to investigators on request from the coordinating center.

AT13387 PK Samples

If AT13387 was not administered at Cycle day 8 or 15, PK samples will only be drawn for dabrafenib/trametinib for that time point.

1. At each time point, collect 4 mL whole blood PK sample into a properly labeled 4 mL Lithium Heparin blood collection tube. Record the date and time each sample is collected. **Note the sampling time and volume of blood collection may differ with specific protocols and/or regimens.**
2. Immediately after collection, gently invert (do not shake) the evacuated blood collection tube for 30 seconds, then place on a standard roller for a minimum of 5 minutes. If a blood roller is not available, continue to invert the tube a further 8 – 10 times. Blood samples should be processed into plasma within 1 hour of sample collection
3. Centrifuge the tube at 1100 - 1500g for 10-15 minutes at 4-8° C within 1 hour of

sample collection.

4. Immediately transfer plasma into two 2.0 mL Matrix TrackMate ScrewTop tubes, each containing approximately 0.75 mL of plasma.
5. Store at -20°C until shipped.
6. Ship all frozen plasma samples on dry ice

Details for dabrafenib and trametinib PK collection and process are provided in the “Pharmacokinetic Laboratory Manual”. Note: This manual will be disseminated with the clinical protocol and is also available to investigators on request from the coordinating center.Dabrafenib/Trametinib PK Samples

Due to the potential instability of trametinib, pharmacokinetic blood samples collected for the determination of trametinib/dabrafenib concentration in plasma will be collected in 2 mL K2-EDTA blood tubes.

1. At each time point, collect 2 mL whole blood PK sample into a properly labeled 2mL K2EDTA evacuated blood collection tube. Record the date and time the sample is collected. **(Note the sampling time and volume of blood collection may differ with specific protocols and/or regimens.)**

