13. STATISTICAL CONSIDERATIONS

13.1 Study Design/Endpoints

This is a phase I trial of the combination of dabrafenib, trametinib, and AT13387 in patients with BRAF-mutant advanced solid tumors. The primary objective of the study is to determine the maximum tolerated dose (MTD) of the combination; secondary objectives will provide preliminary estimates of efficacy and toxicity. The escalation and stopping rules imply that the incidence rate for DLT will be less than 33% at the MTD. Following the identification of the MTD, an additional 14 patients will be enrolled in a dose expansion cohort at the MTD.

Toxicities and lab values will be graded according to the NCI Common Toxicity Criteria for Adverse Events (v4.0). Dose-limiting toxicities will be scored and will be defined as in Section 5.2.

Dose escalation will use a standard “3+3” approach, beginning in dose level 1, with dosing and rules for escalation and de-escalation described in the tables below. Tolerability assessments will be based on cycle 1 alone. The MTD is defined as the highest dose level at which 0 or 1 of six patients has experienced a DLT. If an excessive number of toxicities occur at the initial dose level 1, the dose will be reduced to the fall-back dose of -1. If dose level -1 has excessive toxicity, the study will stop.

Dose Level	Dabrafenib [BID/PO]	Trametinib [QD/PO]	AT13387 [D1,8,15/IV]
-1	75 mg	1 mg	180 mg/m ²
1	150 mg	1 mg	180 mg/m ²
2	150 mg	2 mg	180 mg/m ²
3	150 mg	2 mg	220 mg/m ²
4	150 mg	2 mg	260 mg/m ²

Number of Patients with DLT at a Given Dose Level	Dose Escalation Rule
0 out of 3	Proceed to the next dose level and enroll 3 patients
1 out of 3	Enroll and treat 3 additional patients at this dose level
	Dose escalation will be stopped. The MTD will be one dose below this dose

≥ 2 out of 3	level. Three (3) additional patients will be entered at the next lower dose level if only 3 patients were treated previously at that dose.
1 out of 6	Proceed to the next dose level.
≥ 2 out of 6	se escalation will be stopped. The MTD will be one dose below this dose level. Three (3) additional patients will be entered at the next lower dose level if only 3 patients were treated previously at that dose.

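### The calendar's waiver of Day 8 and Day 15 assessments for patients off AT13387 makes no exception for cycle 1, so some patients still being scored for DLT lose scheduled safety labs

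*Combined protocol and SAP*

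**What the plan says.** The Section 10 introduction states: "Patients who are not being treated with AT13387 do not need to have Day 8 and Day 15 assessments done". Footnote 4 repeats the waiver: "Day 8 and Day 15 assessments are not required for patients who are not receiving AT13387 infusions". In the calendar, the footnote 4 mark sits on the Cycle 1 Day 8 and Day 15 columns. The same footnote says what those visits contain: physical exam, history, concurrent medications, vital signs, ECOG status and laboratory work, with the instruction that "Hematology and Blood Chemistry panels will be completed prior to Day 8 and Day 15 treatment".

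Those two visits lie inside the window that decides escalation. Section 5.2: "DLT refers to toxicities experienced during the first cycle of treatment between days 1-28". Section 13.1: "Tolerability assessments will be based on cycle 1 alone".

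Section 5.1.3 provides that an AT13387 dose that cannot be given on Day 8 or 15 is skipped, not delayed. Section 6.1 lets dabrafenib and trametinib continue when AT13387 is stopped for toxicity. Section 11.1.1 makes every patient evaluable for toxicity from first treatment. Section 13.1 replaces a patient when DLT cannot be assessed because of rapid progression, or when treatment stops in cycle 1 for reasons other than toxicity. Neither section sets a minimum set of cycle 1 assessments.

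**The concern.** The primary endpoint is the MTD, and it rests on DLT counts among three or six patients per level. Several DLT criteria depend on a measured laboratory value: any Grade 4 toxicity other than lymphopenia, and Grade 3 electrolyte events not resolved by replacement within 24 hours. An asymptomatic event of this kind is seen only if blood is drawn. The waiver removes the scheduled draw from patients whose DLT clock is still running, and it does so because an infusion was missed. A DLT that is not measured is scored as no DLT. At this sample size, one such miss can turn 1 of 3 into 0 of 3, or 2 of 6 into 1 of 6, and so change the escalation decision.

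**Working it through.** **1. Who is left in the gap.** Section 5.2 states: "Intolerable AEs are toxicities deemed to lead to a missing dose of AT13387 or more than 25% of dabrafenib/trametinib in the first cycle". It also lists as a DLT: "Grade 3 (or grade 2 intolerable) non-hematologic toxicity". So a related non-hematologic toxicity of grade 2 or higher that causes a missed infusion is generally a DLT already, subject to the listed exemptions, and later labs cannot change that patient's score. Three groups remain:

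- An infusion skipped for logistics while the oral drugs continue. Section 13.1 does not say whether this counts as treatment being stopped.
- AT13387 interrupted under Table 6-15 for a Grade 3 hematologic event that is not a DLT: neutropenia without fever, or thrombocytopenia without clinically significant bleeding.
- AT13387 interrupted under Table 6-15 for an exempt short-lived Grade 3 event, such as nausea, vomiting or diarrhea lasting no more than 72 hours.

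**2. Length of the scheduled gap** (nominal days; Cycle 2 Day 1 = Day 29):

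- Full schedule: longest gap 29 − 15 = 14 days.
- Day 15 waived: 29 − 8 = 21 days.
- Day 8 and Day 15 both waived: 29 − 1 = 28 days.

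Panels are drawn before that day's treatment, so a hold decided at Day 8 normally comes after the Day 8 draw. The usual figure is therefore 21 days.

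**3. Are laboratory events plausible?** The dabrafenib-trametinib table in Section 2.2.2.4 gives these Grade 3-4 rates:

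| Event | 150/2 | 150/1 |
|---|---|---|
| Neutropenia | 13% | 2% |
| Hyponatremia | 11% | 15% |
| Hypophosphatemia | 5% | 11% |

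Sodium, phosphorus and CBC are in the calendar's panel (footnote g). These are on-study rates, not cycle 1 rates, so they show plausibility and nothing more.

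**4. The plan's own table.** With DLT rate p and q = 1 − p, escalation needs 0/3, or 1/3 followed by 0/3:

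P(escalate) = q³ + 3pq² × q³ = q³ + 3pq⁵.

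- p = 0.30: 0.343 + 0.151 = 0.494 (plan: 0.49).
- p = 0.40: 0.216 + 0.093 = 0.309 (plan: 0.31).

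The other four entries also reproduce: 0.906, 0.709, 0.172 and 0.082.

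**5. Illustration with unseen DLTs.** Replace p by p(1 − u), where u is the share of DLTs not seen. The documents give no value for u. The range used is:

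- u = 3%: 10% of patients under the waiver × 30% of their DLTs laboratory-only.
- u = 20%: 20% of patients under the waiver, none of their DLTs seen.

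| u | True rate 0.30: seen rate → P(escalate) | True rate 0.40: seen rate → P(escalate) |
|---|---|---|
| 0 | 0.300 → 0.49 | 0.400 → 0.31 |
| 3% | 0.291 → 0.51 | 0.388 → 0.33 |
| 10% | 0.270 → 0.56 | 0.360 → 0.38 |
| 20% | 0.240 → 0.62 | 0.320 → 0.45 |

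**The case against.** A reader might infer that any patient whose AT13387 is held or stopped can pass through the window unmonitored and be counted DLT-free. The documents do not support that. Most related non-hematologic holds of grade 2 or higher are already DLTs, and a patient whose treatment stops for other reasons is replaced. AE assessment runs throughout the study (Section 10, footnote n). Creatinine rises and ALT elevations have their own recheck intervals (Tables 6-5 and 6-14). All of this stands and narrows the point. What it does not cover is an asymptomatic blood count or electrolyte value: AE collection cannot find a value nobody measured, and Table 6-15 asks for close monitoring without an interval.

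A reader might also cite the Grade 3 laboratory values that are exempt if back to baseline within 7 days. That example runs the other way: without a repeat test the exemption is not shown, and the event stays a DLT.

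The neutropenia example has limits too. If Grade 3 neutropenia is attributed to the oral agents, Table 6-1 interrupts them as well, and Section 6 modifies every agent when attribution is unclear. Restart requires resolution, hence a repeat count. But the DLT window keeps running, no date is set for that count, and a count taken at recovery need not show an intervening Grade 4 value.

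Finally, the wording in the Section 10 introduction can be read as covering only patients permanently off AT13387. Section 9.2.1.2 describes a single missed dose differently: "If AT13387 was not administered at Cycle day 8 or 15, PK samples will only be drawn for dabrafenib/trametinib for that time point". That reading would shrink the group, but footnote 4 does not settle it.

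**Conclusion.** The point holds in a narrow form. A stated rule removes scheduled primary-endpoint labs from some patients who still count for DLT, and no evaluability rule excludes them. The direction is certain, since a missed DLT can only favour escalation. The size is not known: the documents give neither the share of patients off AT13387 in cycle 1 nor the share of DLTs that are laboratory-only.

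The increases shown (to about 0.51-0.62 at a true 30% rate and 0.33-0.45 at 40%) rest on the assumed 3% to 20% of unseen DLTs and treat misses as independent across patients. The low end is small. They do not demonstrate that the MTD will be set too high. This is an inexpensive improvement worth making.

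**What to change.** In the Section 10 introduction and footnote 4, limit the waiver to cycle 2 onward. In cycle 1, collect the Day 8 and Day 15 AE assessment, vital signs, hematology and chemistry from every patient still in the DLT window, whatever the AT13387 status. In Section 13.1, add that a patient without a DLT who is missing these assessments is not counted as DLT-free.

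The cost is a short amendment, at most two routine visits with labs for the few patients off AT13387 in cycle 1, and an occasional replacement patient. On Day 15 the added burden is smaller still, because Section 9.2.1.2 already keeps the dabrafenib/trametinib PK draw when the infusion is missed.

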11. MEASUREMENT OF EFFECT

Although response is not the primary endpoint of the phase I portion of this trial, patients with measurable disease will be assessed by standard criteria. For the purposes of this study, patients should be re-evaluated every 8 weeks. In addition to a baseline scan, confirmatory scans will also be obtained at least 4 weeks following initial documentation of an objective response. Every attempt should be made to use a consistent imaging modality for each individual participant.

11.1 Antitumor Effect – Solid Tumors

For the purposes of this study, patients should be re-evaluated for response every 8 weeks. In addition to a baseline scan, confirmatory scans should also be obtained not less than 4 weeks following initial documentation of objective response.

Response and progression will be evaluated in this study using the new international criteria proposed by the revised Response Evaluation Criteria in Solid Tumors (RECIST) guideline (version 1.1) [Eur J Ca 45:228-247, 2009]. Changes in the largest diameter (unidimensional measurement) of the tumor lesions and the shortest diameter in the case of malignant lymph nodes are used in the RECIST criteria.

11.1.1 Definitions

Evaluable for toxicity. All patients will be evaluable for toxicity from the time of their first treatment with trametinib, dabrafenib, and AT13387.

Evaluable for objective response. Only those patients who have measurable disease present at baseline, have received at least one cycle of therapy, and have had their disease re-evaluated will be considered evaluable for response. These patients will have their response classified according to the definitions stated below. (Note: Patients who exhibit objective disease progression prior to the end of cycle 1 will also be considered evaluable.)

Evaluable Non-Target Disease Response. Patients who have lesions present at baseline that are evaluable but do not meet the definitions of measurable disease, have received at least one cycle of therapy, and have had their disease re-evaluated will be considered evaluable for non-target disease. The response assessment is based on the presence, absence, or unequivocal progression of the lesions.

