11.1.4.3 Evaluation of Best Overall Response

The best overall response is the best response recorded from the start of the treatment until disease progression/recurrence (taking as reference for progressive disease the smallest measurements recorded since the treatment started). The patient's best response assignment will depend on the achievement of both measurement and confirmation criteria.

For Patients with Measurable Disease (*i.e.*, Target Disease)

Target Lesions	Non-Target Lesions	New Lesions	Overall Response	Best Overall Response when Confirmation is Required*
CR	CR	No	CR	≥ 4 wks. Confirmation**
CR	Non-CR/Non-PD	No	PR	≥ 4 wks. Confirmation**
CR	Not evaluated	No	PR	
PR	Non-CR/Non-PD/not evaluated	No	PR	Documented at least once ≥ 4 wks. from baseline**
SD	Non-CR/Non-PD/not evaluated	No	SD	
PD	Any	Yes or No	PD	no prior SD, PR or CR
Any	PD***	Yes or No	PD	
Any	Any	Yes	PD	

* See RECIST 1.1 manuscript for further details on what is evidence of a new lesion.

** Only for non-randomized trials with response as primary endpoint.

*** In exceptional circumstances, unequivocal progression in non-target lesions may be accepted as disease progression.

Note: Patients with a global deterioration of health status requiring discontinuation of treatment without objective evidence of disease progression at that time should be reported as “*symptomatic deterioration*.” Every effort should be made to document the objective progression even after discontinuation of treatment.

For Patients with Non-Measurable Disease (*i.e.*, Non-Target Disease)

Non-Target Lesions	New Lesions	Overall Response
CR	No	CR
Non-CR/non-PD	No	Non-CR/non-PD*
Not all evaluated	No	not evaluated
Unequivocal PD	Yes or No	PD
Any	Yes	PD

* ‘Non-CR/non-PD’ is preferred over ‘stable disease’ for non-target disease since SD is increasingly used as an endpoint for assessment of efficacy in some trials so to assign this category when no lesions can be measured is not advised

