If $\geq 2/3$ or $\geq 2/6$ patients at dose level 1 experience dose limiting toxicities, dose level -1 will be enrolled. If dose level -1 proves too toxic, the study will stop.	Dose escalation will be stopped. The MTD will be one dose below this dose level. Three (3) additional patients will be entered at the next lower dose level if only 3 patients were treated previously at that dose.

The following table shows the probability of escalating the dose for various true, but unknown, rates of unacceptable toxicity.

True DLT Rate	Probability of Dose Escalation
0.10	0.91
0.20	0.71
0.30	0.49
0.40	0.31
0.50	0.17
0.60	0.08

A patient will be replaced if determination of DLT cannot be adequately assessed because of rapid disease progression or if treatment is stopped during the first cycle of therapy for reasons other than toxicity.

When the MTD had been determined, a total of 14 patients will be enrolled in an expansion cohort of patients with BRAF-mutant advanced solid tumors to obtain preliminary toxicity and efficacy estimates. Patients treated at the MTD during the dose escalation phase may be included in the expansion cohort. Toxicity and efficacy rates will be summarized with 90% exact binomial confidence intervals. For a sample of size 14, the confidence intervals will be no wider than 0.48.

The table below summarizes the probabilities of observing at least one patient with a severe or unexpected toxicity in the expansion cohort for a range of incidence rates.

True Incidence of Unexpected or Severe Toxicity	Probability of Observing One or More Patients with Toxicity among 14
0.01	0.13
0.03	0.35
0.05	0.51
0.08	0.69
0.09	0.73
0.10	0.77
0.15	0.90

Secondary endpoints that will be assessed for the 14 patients treated at the MTD are: objective response rate, progression-free survival (PFS), 6-month PFS, and 1-year overall survival (OS).

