Objective response rate is defined as the proportion of patients with complete or partial response as their best response to therapy. At the time of each restaging, patients will be classified as achieving complete response (CR), partial response (PR), stable disease (SD), progressive disease (PD), or non-evaluable for response according to RECIST (Version 1.1) criteria. Objective response will be determined by the best overall response designation recorded between the date of first dose of trial therapy and the date of objectively documented disease progression or cessation of trial therapy, whichever occurs first. For patients without documented progression or cessation of trial therapy, all available response designations will contribute to the objective response determination.

The distributions of progression-free survival (PFS) and overall survival (OS) will each be summarized using the product-limit method of Kaplan-Meier. Median times for each endpoint will be presented with two-sided, 90% confidence intervals estimated using log(-log(survival)) methodology. Kaplan-Meier estimates of 6-month PFS and 1-year OS will also be presented with two-sided, 90% confidence intervals.

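### Sections 11.1.1 and 13.1 give different patient sets for the objective response rate, and nothing says how a non-evaluable patient counts

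*Combined protocol and SAP*

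**What the plan says.** Section 11.1.1 sets the response-evaluable group: only patients with measurable disease at baseline who "have received at least one cycle of therapy, and have had their disease re-evaluated will be considered evaluable for response", and it is this group whose response is then classified. One exception is added: "Note: Patients who exhibit objective disease progression prior to the end of cycle 1 will also be considered evaluable".

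Section 13.1 describes the analysis differently. It states: "Secondary endpoints that will be assessed for the 14 patients treated at the MTD are: objective response rate", followed by the time-to-event endpoints. It then says: "Objective response rate is defined as the proportion of patients with complete or partial response as their best response to therapy". At each restaging a patient is placed in one of several classes, the last of which are "progressive disease (PD), or non-evaluable for response according to RECIST (Version 1.1) criteria". On precision it says: "Toxicity and efficacy rates will be summarized with 90% exact binomial confidence intervals", and it gives 0.48 as the greatest width for a sample of 14.

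Section 13.3 repeats the exact 90% interval for the response rate without naming a denominator. Section 11.1.4.3 has its own label, symptomatic deterioration, for clinical decline: "Patients with a global deterioration of health status requiring discontinuation of treatment without objective evidence of disease progression at that time should be reported as" falling under that label. It does not say how that outcome enters the ORR.

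**The concern.** The two sections support two different calculations. Under 13.1 the divisor is 14, and a non-evaluable patient presumably stays in it. Under 11.1.1 a patient who does not meet the rule has no response classification and could be left out of the divisor. An analyst could follow either and claim to have followed the protocol.

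The choice matters because the 11.1.1 rule selects on what happens after treatment starts. The patients at risk of removal are those who die, deteriorate or stop before completing cycle 1 without objective progression, and those who are never re-imaged. They have essentially no recorded responses, so removing them can only raise the rate. If the choice is left until the data are known, it can be made with the answer in view. ORR is a named secondary objective (1.1.2.1), and with 14 patients each exclusion moves it by several percentage points.

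**Working it through.** **Inputs.** From 13.1: n = 14, exact binomial intervals at 90%, stated maximum width 0.48. I take the intervals as two-sided Clopper-Pearson. From 11.1.1: the evaluability rule and its exception. From the Section 10 calendar: scans at odd cycles, so the first scheduled one is near day 1 of cycle 3, after 2 x 28 = 56 days. Not in the documents, so assumed: the number m removed under 11.1.1 (0 to 4) and the number of responders r.

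**Step 1: reproduce the plan's figure.** For x responders of n, the lower limit is the 5% quantile of Beta(x, n - x + 1) and the upper limit is the 95% quantile of Beta(x + 1, n - x). At n = 14 the widest interval is at x = 7: 0.264 to 0.736, width 0.473. This agrees with the stated limit of 0.48.

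**Step 2: the same limit on a smaller denominator.**

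| n | maximum 90% width | within 0.48? |
|---|---|---|
| 14 | 0.473 | yes |
| 13 | 0.489 | no |
| 12 | 0.509 | no |
| 11 | 0.529 | no |
| 10 | 0.555 | no |

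One exclusion is enough to break the guarantee. These are worst cases over x; a particular result may be narrower.

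**Step 3: shift in ORR.** If the m patients removed include no responder, 13.1 gives r/14 and 11.1.1 gives r/(14 - m). The ratio is 14/(14 - m), whatever r is.

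| m | ratio | r = 4 (90% CI) | r = 6 (90% CI) |
|---|---|---|---|
| 0 | 1.00 | 28.6% (10.4 to 54.0) | 42.9% (20.6 to 67.5) |
| 1 | 14/13 = 1.08 | 30.8% (11.3 to 57.3) | 46.2% (22.4 to 71.3) |
| 2 | 14/12 = 1.17 | 33.3% (12.3 to 60.9) | 50.0% (24.5 to 75.5) |
| 3 | 14/11 = 1.27 | 36.4% (13.5 to 65.0) | 54.5% (27.1 to 80.0) |
| 4 | 14/10 = 1.40 | 40.0% (15.0 to 69.6) | 60.0% (30.4 to 85.0) |

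**Step 4: who would be removed under 11.1.1.**
- Objective progression before cycle 1 ends: kept, by the exception.
- Cycle 1 completed, treatment then stopped, scan at the end-of-treatment visit (Section 10) or in follow-up to progression (5.5): kept, because any re-evaluation satisfies the rule.
- Less than one cycle and no objective progression in that time: removed, even if scanned later.
- Cycle 1 completed but death or decline before any repeat scan: removed.

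**The case against.** The best case for the plan is that 13.1 is the statistical section and already answers the question. It names the 14 patients, defines ORR as a proportion of patients rather than of evaluable patients, and keeps non-evaluable as a class to which patients are assigned. Its 0.48 limit works only with all 14. On this view 11.1.1 is measurement language that was never meant as a denominator. Much of this stands: all 14 is the more natural reading.

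A reader might therefore go too far the other way and infer that the plan removes everyone who leaves before the week-8 scan and that its ORR is biased upward. The documents do not support that. Section 11.1.1 never says its set is the ORR denominator. It asks for a re-evaluation, not the week-8 scan in particular. The end-of-treatment scan and follow-up under 5.5 keep some early leavers evaluable, and 11.1.4.3 asks sites to try to document objective progression after treatment stops.

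The objection does not remove the conflict. No text ranks 13.1 above 11.1.1, none says that a non-evaluable patient is a non-responder, and 13.3 is silent on the denominator. The rescue routes do not reach patients who die or are too ill to scan, or those who stop within cycle 1 without objective progression.

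**Conclusion.** The two sections conflict and should be reconciled before analysis. Upward bias is conditional: it arises only if the 11.1.1 set is used as the denominator. Its size would then be 14/(14 - m), or 1.08 to 1.40 for m = 1 to 4, assuming no responder is among those removed; with m = 0 there is none. The documents give no early-exit rate, so the range for m is an assumption and the true size is unknown. The stated precision holds only with all 14 in the denominator, which favours resolving the conflict that way. ORR is secondary and descriptive, with no test or threshold attached, so the MTD decision does not depend on it.

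**What to change.** State the following in 11.1.1, 13.1 and 13.3:

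- The ORR denominator is all patients treated at the MTD in the expansion set. Measurable disease needs no extra condition, because 3.1.2 already requires it at entry.
- Patients who are non-evaluable, or have no post-baseline assessment for any reason, count as non-responders.
- How patients replaced under the DLT rule in 13.1 are counted. That rule replaces patients whose DLT status cannot be assessed because of rapid progression, or who stop in cycle 1 for reasons other than toxicity. Patients treated at the MTD during escalation may enter the expansion cohort, so the question can arise.
- Any result on the 11.1.1 evaluable set is a supportive display only.

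The cost is a few sentences and no new data. The reported ORR may be slightly less favourable.
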